7.1 End of Therapy & Follow-up

STUDIES TO BE OBTAINED	End of Therapy
History	X
Physical exam with VS	X
Performance status	X
CBC, differential, platelets	X
Electrolytes including Ca ⁺⁺ , PO ₄ , Mg ⁺⁺	X
Creatinine, SGPT, bilirubin	X
Total protein/albumin	X
Tumor disease evaluation (see Section 16.0)	X

See COG Late Effects Guidelines for recommended post treatment follow-up:

<http://www.survivorshipguidelines.org/>

Note: Follow-up data must be submitted in accordance with the Case Report Forms (CRFs) schedule.

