Patients who are not evaluable for both disease control and response evaluation may be replaced for the purposes of the statistical rule.

9.5 **Evaluability for Toxicity**

Tolerability of CDX-011 - An eligible patient will be considered for toxicity monitoring if one of the following occurs: (1) complete one cycle of CDX-011 prior to receiving non-protocol anticancer therapy; (2) die on protocol therapy for a reason considered possibly, probably or likely related to CDX-011; or (3) are removed from protocol therapy because of an adverse experience possibly, probably or likely related to CDX-011. A toxicity-evaluable patient will be considered in the analysis during the interval from study enrollment until the termination of protocol therapy. A toxicity-evaluable patient will be considered to have experienced an excessive toxicity event if: (1) the patient dies on protocol therapy for a reason considered possibly, probably or likely related to; or (2) experiences a dose-limiting toxicity (DLT). DLTs will be as defined in [Section 5.1.1](#) of the protocol:

The analytic unit for monitoring for excessive toxicity will be the patient-cycle: Each cycle where the patient receives CDX-011 and does not receive non-protocol anticancer therapy will be considered in the analysis. If there is overwhelming evidence that the dose selected for this trial has a per-cycle-DLT probability of more than 30%, we will identify the regimen to the COG DSMC, Bone Tumor Committee leadership and CTEP as associated with a toxicity profile that may require modification of the regimen. We will use a Bayesian rule to monitor for excessive toxicity. We will assume a beta prior to distribution with $\alpha=0.6$ and $\beta=1.4$. If this posterior probability of the chance of DLT is at least 30% exceeds 80%, we will identify the regimen to the COG DSMC, Bone Tumor leadership and CTEP as associated with a toxicity profile that may require modification of the regimen.

9.6 **Estimation of Disease Control and RECIST Response Rates**

$P(R)$ and $P(S)$ for each cohort defined by prior eribulin exposure will be estimated using the maximum likelihood estimates, *viz.*,

$$P(R) \hat{=} \hat{p}_R = \frac{\text{Number of Patients Considered as PR or CR}}{\text{Number of Evaluable Patients in Cohort}};$$

$$P(S) \hat{=} \hat{p}_S = \frac{\text{Number of Patients With Disease Control at 4 Months}}{\text{Number of Evaluable Patients in Cohort}}$$

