11.7 General Instructions for Expedited Reporting via CTEP-AERS

The descriptions and grading scales found in the NCI Common Terminology Criteria for Adverse Events (CTCAE) version 4.0 will be utilized for AE reporting and are located on the CTEP website at:

http://ctep.cancer.gov/protocolDevelopment/electronic_applications/ctc.htm. All appropriate treatment areas should have access to a copy of the CTCAE.

An expedited AE report for all studies utilizing agents under an NCI IND/IDE must be submitted electronically to NCI via CTEP-AERS at: <https://eapps-ctep.nci.nih.gov/ctepaers>

In the rare situation where Internet connectivity is disrupted, the 24-hour notification is to be made to the NCI for agents supplied under a CTEP IND by telephone call to [contact].

In addition, once Internet connectivity is restored, a 24-hour notification that was phoned in must be entered into the electronic CTEP-AERS system by the original submitter of the report at the site.

- Expedited AE reporting timelines are defined as:
 - **24-Hour; 5 Calendar Days** - The AE must initially be reported via CTEP-AERS within 24 hours of learning of the event, followed by a complete expedited report within 5 calendar days of the initial 24-hour report.
 - **7 Calendar Days** - A complete expedited report on the AE must be submitted within 7 calendar days of the investigator learning of the event.
- Any event that results in a persistent or significant incapacity/substantial disruption of the ability to conduct normal life functions, or a congenital anomaly/birth defect, or is an IME, which based upon the medical judgment of the investigator may jeopardize the patient and require intervention to prevent a serious AE, must be reported via CTEP-AERS **if the event occurs following investigational agent administration**.
- Any death occurring within 30 days of the last dose, regardless of attribution to an agent/intervention under an NCI IND/IDE requires expedited reporting **within 24 hours**.
- Any death occurring greater than 30 days of the last dose with an attribution of possible, probable, or definite to an agent/intervention under an NCI IND/IDE requires expedited reporting **within 24 hours**.

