11.8 Reporting Table for Late Phase 2 and Phase 3 Studies

Expedited Reporting Requirements for Adverse Events that Occur on Studies under an IND/IDE within 30 Days of the Last Administration of the Investigational Agent/Intervention¹

FDA REPORTING REQUIREMENTS FOR SERIOUS ADVERSE EVENTS (21 CFR Part 312)

NOTE: Investigators **MUST** immediately report to the sponsor (NCI) **ANY** Serious Adverse Events, whether or not they are considered related to the investigational agent(s)/intervention (21 CFR 312.64). An adverse event is considered serious if it results in **ANY** of the following outcomes:

- 1) Death.
- 2) A life-threatening adverse event.
- 3) Any AE that results in inpatient hospitalization or prolongation of existing hospitalization for ≥ 24 hours. This does not include hospitalizations that are part of routine medical practice.
- 4) A persistent or significant incapacity or substantial disruption of the ability to conduct normal life functions.
- 5) A congenital anomaly/birth defect.
- 6) Important Medical Events (IME) that may not result in death, be life threatening, or require hospitalization may be considered serious when, based upon medical judgment, they may jeopardize the patient or subject and may require medical or surgical intervention to prevent one of the outcomes listed in this definition. (FDA, 21 CFR 312.32; ICH E2A and ICH E6.)

ALL SERIOUS adverse events that meet the above criteria **MUST** be immediately reported to the NCI via CTEP-AERS within the timeframes detailed in the table below.

Hospitalization	Grade 1 Timeframes	Grade 2 Timeframes	Grade 3 Timeframes	Grade 4 & 5 Timeframes
Resulting in Hospitalization ≥ 24 hrs		7 Calendar Days		24-Hour Notification
Not resulting in Hospitalization ≥ 24 hrs	Not Required		7 Calendar Days	5 Calendar Days

NOTE: Protocol specific exceptions to expedited reporting of serious adverse events are found in the Specific Protocol Exceptions to Expedited Reporting (SPEER) portion of the CAEPR. Additional Special Situations as Exceptions to Expedited Reporting are listed below.

Expedited AE reporting timelines are defined as:

“24-Hour; 5 Calendar Days” - The AE must initially be reported via CTEP-AERS within 24 hours of learning of the AE, followed by a complete expedited report within 5 calendar days of the initial 24-hour notification.

“7 Calendar Days” - A complete expedited report on the AE must be submitted within 7 calendar days of learning of the AE.

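### The Section 9.5 toxicity monitor stops counting when protocol therapy ends but keeps the last dosed cycle in its denominator, so related DLTs and deaths soon after removal are not scored

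*Combined protocol and SAP*

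**What the plan says.** Section 9.5 sets the counting window: "A toxicity-evaluable patient will be considered in the analysis during the interval from study enrollment until the termination of protocol therapy". It adds no days after the last dose, and the available text does not define the date of termination (last dose, end of the final cycle, or date of the decision). An excessive toxicity event is either a DLT or a death, and the death limb reads "the patient dies on protocol therapy for a reason considered possibly, probably or likely related to" (the sentence breaks off there).

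The unit of analysis is the patient-cycle: "Each cycle where the patient receives CDX-011 and does not receive non-protocol anticancer therapy will be considered in the analysis". The rule uses a Beta(0.6, 1.4) prior on the per-cycle DLT probability. The regimen is referred to the DSMC, the Bone Tumor Committee leadership and CTEP when the posterior probability of a rate of at least 30% exceeds 80%.

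The reporting sections look further. Section 11.7 states: "Any death occurring within 30 days of the last dose, regardless of attribution to an agent/intervention under an NCI IND/IDE requires expedited reporting". The Section 11.8 table covers serious events "within 30 Days of the Last Administration of the Investigational Agent/Intervention". Sections 11.3.1 and 11.3.3 extend reporting to related serious events and related deaths after 30 days. Section 8.1 requires follow-up after protocol therapy ends.

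**The concern.** The numerator and the denominator of the rule do not close together. Take a patient dosed on Day 1 of Cycle 2, taken off for progression on Day 8, who dies of a possibly related cause on Day 13 without having started other therapy. The death must be reported within 24 hours. Under Section 9.5 it falls after termination and is not a death on protocol therapy, so the rule does not count it. The Cycle 2 dose was given, so the cycle is counted and scores as free of DLT.

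Nothing in the documents brings such an event back into the Bayesian rule. Section 8.1 allows removal at any time for progression, refusal, physician decision, or surgery or radiation to measurable disease. With a historical 4-month EFS of 12% (Section 2.1), many patients can be expected to leave early. At stake is whether the one formal toxicity rule that runs through the whole trial flags a regimen whose per-cycle DLT rate is above 30%.

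**Working it through.** The plan gives no operating characteristics for the toxicity monitor, so there is no stated figure to reproduce.

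**1. Days lost.** Inputs: 21-day cycle with dosing on Day 1 (Section 4.2); 30-day reporting window (Section 11.8). Thirty days after a Day 1 dose is Day 31.

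| Termination read as | Days of the 30 not counted |
|---|---|
| End of the completed 21-day cycle | 30 − 21 = 9 |
| Day 21, the day of the scheduled scan | 31 − 21 = 10 |
| Day 8 (mid-cycle removal) | 31 − 8 = 23 |
| The last dose itself | 30 |
| Patient still on protocol therapy during a long hold | 0 |

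**2. What one lost event does.** With x DLT cycles in n patient-cycles the posterior is Beta(0.6 + x, 1.4 + n − x), and the flag needs P(p ≥ 0.30) > 0.80. For selected n, the smallest x that flags, and the posterior with one event fewer:

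| n | x at boundary | P with x | P with x − 1 |
|---|---|---|---|
| 20 | 8 | 0.807 | 0.658 |
| 38 | 14 | 0.801 | 0.694 |
| 76 | 27 | 0.840 | 0.774 |
| 114 | 39 | 0.826 | 0.770 |

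At each of these n, one uncounted event at the boundary takes the posterior below 0.80 and removes the flag.

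**3. Sensitivity over the trial (illustrative).** A simulation used 38 patients, with a look after each patient from the sixth and 3,000 runs per setting. These inputs are assumptions, not document figures:
- cycles per patient of 2, 4, 6, 9 or 18 with probabilities 0.65, 0.20, 0.08, 0.05 and 0.02 (mean 3.39, so final cycles are about 30% of all patient-cycles);
- a constant per-cycle DLT risk;
- a share m of final-cycle DLTs lost to the window, with m = 0 standing for full counting.

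Probability that the monitor flags at some look:

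| True rate per cycle | m = 0 | m = 0.1 | m = 0.3 | m = 0.5 |
|---|---|---|---|---|
| 0.35 | 82% | 76% | 63% | 47% |
| 0.40 | 97% | 96% | 89% | 78% |
| 0.45 | 99.9% | 99.5% | 98% | 94% |

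At a true rate of 0.35 the mean observed rate falls from 0.349 (m = 0) to 0.339, 0.318 and 0.299.

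**4. Would a flat 30-day cutoff do?** No. Section 5.1.1.1 makes myelosuppression that delays the next cycle by more than 14 days a DLT. The next cycle is due on Day 22, so this DLT is established only after Day 22 + 14 = Day 36, more than 35 days after the dose. The current text counts it while the patient remains on protocol therapy; a cutoff fixed at 30 days would drop it if treatment is not resumed.

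**The case against.** The strongest reply is that scheduled disease imaging falls on Day 21, so removal for progression at a scheduled scan comes at the end of a completed cycle. Events within that cycle are then counted and only the tail is lost. The patient-cycle sentence also supports counting the whole final cycle. This stands. A reader might infer that late events throughout every patient's final cycle are excluded; the documents do not support that. Loss within the cycle needs mid-cycle removal, or termination read as the last dose.

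The denominator point is not universal either. If the patient starts other anticancer therapy within the cycle, the patient-cycle sentence can be read as dropping that cycle.

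Reporting is also less complete than Section 11.8 alone suggests. Section 11.9 exempts Grade 1 to 4 myelosuppression from expedited reporting, and Section 11.10 gives no end date for routine reporting. A late hematologic DLT may therefore not be captured at all, so the claim that the data are already in hand is firm only for deaths and for serious events outside the listed exceptions.

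Finally, the rule only notifies. Section 12.2 has unexpected frequencies of serious events brought to the DSMC by another route. A reader might infer that late related deaths escape all oversight, or that the Aim 1.2.1 toxicity profile is confined to the rule's counts; no section says either. The exclusion is from the Section 9.5 rule.

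None of this brings a post-termination event into the rule.

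**Conclusion.** The point holds in this limited form: as written, Section 9.5 leaves related DLTs and deaths after termination out of the Bayesian rule while normally keeping the cycle in the denominator. The direction is certain (toward missing excess toxicity); the size is not. The calendar gap is about 9 to 10 days for removal at the end of a cycle and up to 30 under the narrowest reading of termination. The boundary calculation is exact given the stated prior and trigger. The simulated loss of sensitivity depends on an assumed m and assumed treatment durations, and shows a range, not a prediction.

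A reader might also take the share of patient-cycles that are a patient's last as the share of DLTs missed. With scans every two cycles (42 days = 1.38 months), a constant hazard and no cap, 12% event-free at 4 months gives retention per two cycles of 0.12^(1.38/4) = 0.481. The final-cycle share is then (1 − 0.481)/2 = 26%. At the plan's 20% disease control rate it is (1 − 0.574)/2 = 21%. Those figures do not measure the defect: the model has every exit at a Day 21 scan, where no in-cycle events are lost. The documents give no share of DLTs arising after termination.

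This should be corrected because the change is cheap and the bias runs one way.

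**What to change.** Amend Section 9.5 as follows:

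- Count each toxicity-evaluable patient from enrollment until the later of termination of protocol therapy and 30 days after the last dose of CDX-011, or until the start of non-protocol anticancer therapy if that is earlier. The later-of rule keeps the Section 5.1.1.1 cycle-delay DLT.
- Define the date of termination of protocol therapy.
- Count deaths possibly, probably or definitely related to CDX-011 even if they occur after removal from protocol therapy.
- Assign late events to the last dosed cycle, and make the patient-cycle sentence agree with this.
- Align the attribution terms with Section 5.1.1, which uses definitely where Section 9.5 has likely.
- State that DLT-level hematologic events are collected on the routine AE form through this window, since Section 11.9 exempts Grade 1 to 4 myelosuppression from expedited reporting.

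The cost is mainly wording, with a little more routine AE collection after the last dose. The monitored DLT rate may be slightly higher, so the rule may flag somewhat more often. In the simulation above, at a true rate of 0.25, it flags in 18% of runs with full counting against 14% with m = 0.1.

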5.1.1.1 Hematological Dose Limiting Toxicity

[figure not shown]
- Grade 4 neutropenia for > 7 days
- Grade 4 febrile neutropenia
- Platelet count < 25,000/ μ L on 2 separate days, or requiring a platelet transfusion on 2 separate days, within a 7 day period
- Myelosuppression that causes a delay of > 14 days between treatment cycles.

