8.0 CRITERIA FOR REMOVAL FROM PROTOCOL THERAPY AND OFF STUDY CRITERIA

8.1 Criteria for Removal from Protocol Therapy

- a) Progressive disease.
- b) Unacceptable toxicity due to protocol therapy (see [Section 5.0](#)).
- c) Refusal of further protocol therapy by patient/parent/guardian.
- d) Completion of planned therapy.
- e) Physician determines it is in patient's best interest.
- f) Development of a second malignancy.
- g) Repeat eligibility studies (if required) are outside the parameters required for eligibility (see Section 3.2).
- h) Surgery or radiation performed on any site of measurable disease before the end of the 6th cycle.
- i) Failure to recover from surgery within 6 weeks.
- j) Pregnancy.

Patients who are off protocol therapy are to be followed until they meet the criteria for Off Study (see below). Follow-up data will be required unless patient is taken off study.

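### The per-cycle toxicity monitor in Section 9.5 excludes cycles with non-protocol therapy regardless of order, so read literally it drops a DLT that is followed by a switch within the same 21-day cycle

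*Combined protocol and SAP*

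**What the plan says.** The Bayesian monitor is set out in Section 9.5 (Evaluability for Toxicity). It works on cycles, not patients: "The analytic unit for monitoring for excessive toxicity will be the patient-cycle". One sentence decides which cycles enter: a cycle in which the patient is given CDX-011 and "does not receive non-protocol anticancer therapy will be considered in the analysis".

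The sentences just before it are about patients. A patient is evaluable for toxicity by any of three routes:

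- The first does use order; the patient must "complete one cycle of CDX-011 prior to receiving non-protocol anticancer therapy".
- The second is a death on protocol therapy that is related to CDX-011.
- The third requires no completed cycle; it covers patients who "are removed from protocol therapy because of an adverse experience possibly, probably or likely related to CDX-011".

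An evaluable patient who has a DLT has had an excessive toxicity event. The window is also given per patient: "A toxicity-evaluable patient will be considered in the analysis during the interval from study enrollment until the termination of protocol therapy".

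The prior is Beta(0.6, 1.4). The regimen is referred to the DSMC, Bone Tumor leadership and CTEP if the posterior probability that the per-cycle DLT rate is at least 30% exceeds 80%. The therapy delivery map (Section 4.2.1) gives a cycle length of 21 days. Section 8.1 lists "Unacceptable toxicity due to protocol therapy" as a reason to come off therapy.

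**The concern.** The posterior is computed from cycles, so the cycle sentence determines what is counted. It does not distinguish other therapy given before a DLT, which would cloud attribution, from other therapy given after it, which would not. A patient who has a DLT early in a cycle, comes off CDX-011 and starts other treatment before Day 21 could be evaluable under the third route and yet contribute neither the cycle nor the DLT.

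This exclusion is not neutral. Unacceptable toxicity is a reason to stop, and stopping opens the way to other treatment, so dropped cycles may hold more DLTs than retained ones. The observed rate would then be too low and the alert less likely. This is the plan's continuing excessive-toxicity rule, for an agent that Section 2.4 says has no data in children.

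**Working it through.** **Inputs from the plan.** Prior Beta(0.6, 1.4); flag if P(p ≥ 0.30 | data) > 0.80; unit the patient-cycle; maximum enrollment 38 (Section 9.1). The plan gives no operating characteristics for this monitor, so there is no stated figure to reproduce.

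**Step 1: effect of losing one DLT cycle.** With x DLT cycles among n,

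P(p ≥ 0.30 | x, n) = 1 − F(0.30; 0.6 + x, 1.4 + n − x),

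where F is the beta distribution function. Dropping a DLT cycle turns (x, n) into (x − 1, n − 1). The first parameter falls by 1 and the second is unchanged, so the posterior moves down and never up.

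| All cycles | Posterior | One DLT cycle dropped | Posterior | Flag reversed? |
|---|---|---|---|---|
| 5/10 | 0.880 | 4/9 | 0.782 | yes |
| 8/20 | 0.807 | 7/19 | 0.712 | yes |
| 12/30 | 0.863 | 11/29 | 0.801 | no |
| 15/40 | 0.831 | 14/39 | 0.769 | yes |
| 22/60 | 0.855 | 21/59 | 0.810 | no |

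For 12/30, a second loss (10/28) gives 0.721 and the flag goes.

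**Step 2: effect on the chance of a flag at final data.** This needs assumptions that the documents do not supply: 38 patients; a constant per-cycle DLT rate; a chance of ending therapy of 0.5 after a DLT cycle and 0.3 after any other; and a share q of final cycles containing a switch. The literal rule drops such a cycle whether or not it holds a DLT. Any DLT is taken to precede the switch.

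At a true rate of 0.35:

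- Chance that a cycle is the last: 0.35 × 0.5 + 0.65 × 0.3 = 0.37.
- Expected cycles: 38 / 0.37 = 102.70. Expected DLT cycles: 0.35 × 102.70 = 35.95.
- Share of final cycles with a DLT: 0.175 / 0.37 = 0.473, against 0.35 overall. This gap is the source of the bias.
- q = 5%: 1.90 cycles dropped, 0.90 of them with a DLT; rate (35.95 − 0.90) / (102.70 − 1.90) = 0.348.
- q = 30%: 11.40 cycles dropped, 5.39 of them with a DLT; rate (35.95 − 5.39) / (102.70 − 11.40) = 0.335.

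Simulating this model (40,000 trials per true rate) gives:

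| True rate | All cycles counted | q = 5% | q = 10% | q = 20% | q = 30% |
|---|---|---|---|---|---|
| 0.35 | 0.58 | 0.56 | 0.54 | 0.49 | 0.43 |
| 0.45 | 0.99 | 0.98 | 0.98 | 0.97 | 0.96 |

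The drop is about 0.02 to 0.15 at 35% and at most about 0.03 at 45%.

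**Step 3: check on the remedy.** An obvious repair keeps a cut-short cycle if it holds a DLT and drops it otherwise. Inclusion then still depends on the outcome, now in the other direction. In the same model at a true rate of exactly 30% and q = 30%, the flag probability rises from about 0.19 to about 0.33. The remedy must therefore keep cycles regardless of DLT status.

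**The case against.** The best defence is that Section 9.5, read as a whole, does not intend the loss. Admitting a patient because of removal for a related adverse experience, then deleting that patient's only cycle, would defeat the route. The window closes when protocol therapy ends, and Section 4.1.1.3 bars other antineoplastic agents until then, so a switch of drug normally falls outside the window. On this view the cycle sentence is aimed at contamination while on protocol.

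This is a fair reading, and it rules out a stronger claim that a reader might infer: that the plan definitely discards DLTs that came first. No text says so. But the supporting sentences define patients and their follow-up; none overrides the cycle rule. The first route shows that the authors stated order where they wanted it.

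A reader might also expect the DLT defined as "Myelosuppression that causes a delay of > 14 days between treatment cycles" to be the most exposed. The documents do not support that. The next cycle is due on Day 22, so a delay beyond 14 days can be established only after the 21-day cycle has ended. That DLT would be lost only if the cycle were taken to run to the next dose, which the plan does not say.

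The consequence is also limited. The rule refers the regimen for review and does not stop the trial. Suspected DLTs go to the Study Chair within 24 hours (Section 5.1), the DSMC reviews toxicity reports (Section 12.2), and the feasibility rule in Section 9.2 counts patients with a first-cycle DLT rather than cycles.

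**Conclusion.** The point holds as a defect of wording in one rule. Applied literally, the cycle sentence removes a DLT followed by a switch within the same 21-day cycle, in conflict with the patient-level sentences beside it. Each such loss moves the posterior away from the threshold, and a single one can reverse a flag when the count is close to it.

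The overall effect is uncertain. It rests on the assumed share of same-cycle switches and on the assumption that a DLT makes leaving more likely; if dropped cycles held no more DLTs than the rest, the observed rate would not be biased. Within the assumed range the loss matters when the true rate is just above 30% and is small when toxicity is clearly excessive. The documents do not show that DLTs will in fact be lost, but a prespecified safety rule should not depend on an unwritten reading.

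**What to change.** Replace the cycle sentence in Section 9.5 with:

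> Every cycle in which a toxicity-evaluable patient receives CDX-011 is counted, whether or not a DLT occurs; observation for DLT in that cycle ends at the start of non-protocol anticancer therapy or the end of the cycle, and a DLT with onset before non-protocol therapy counts as an event.

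In the model above, where any DLT precedes the switch, this restores the results in the column with all cycles counted.

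The cost is one sentence, plus DLT onset dates and start dates of other therapy. The prior, the threshold, the DLT definitions and the patient-level routes stay as they are. There is a small downside: a cycle cut short without a DLT counts as a full cycle, which slightly understates the rate. A sensitivity analysis that excludes those cycles would show how much this matters.
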